A large study conducted by the Tufts research team screened 14,000 primary care patients, enrolling a sample of employed adults—286 of whom had depression and another 196 depression-free healthy controls. Subjects were observed for 18 months.(21;22) Though equivalent demographically and occupationally at baseline, depressed workers were found to be limited in their ability to perform basic job tasks at levels that were four times worse than the control groups' and they had triple the mean number absences. In addition, within six months after enrolling in the study, 15% of the depression group became unemployed; five times higher than the control group's job loss rate.(23) Moreover, the impact of depression on employment did not improve significantly over time.

The picture is bleaker for our newest veterans. In a recent study of employed OIF/OEF veterans seen in the Cpl. Michael J. Crescenz VAMC's Behavioral Health Lab (BHL) program, multiple dimensions of job performance were impaired by depression. Work limitations were responsible for average at-work productivity losses of between 9 and 10%; equivalent to the losses seen in civilian employed populations with moderate to severe major depressive disorder (MDD).(3)

Service Delivery Options. To our knowledge, there are no programs tailored specifically to employed veterans with depression who are having trouble at work. Various services exist that address facets of the problem, but care is fragmented and spread among a range of different programs, providers and sectors.

For example, within the Veterans Health Administration (VHA), physicians (psychiatrists and primary care providers) deliver the majority of the care that adults with depression receive. While there have been important gains such as improved access to higher quality diagnosis and treatment, especially in PACT or primary care settings, many physicians (already pressed for time) tend to focus on their patients' symptoms and treatment, not on their work problems. Ultimately, many physicians become involved in their patients' work problems around the time a disability claim is involved-which is sometimes too late to prevent it.

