- J. Describe the Research Questions or Hypotheses (that is, what questions are you trying to address by conducting the research.) The effectiveness of the V-WHI approach will be tested in the context of a randomized controlled trial (RCT). The following hypothesis will be tested: veterans receiving V-WHI will have better work outcomes at time 1 (T1) than the usual care group (BHL only) as measured by at-work productivity loss known as presenteeism. A sub-hypothesis for Aim 1 is that the V-WHI effect at T1 will be sustained at least until the final follow-up (T2). Secondary T1 outcome measures expected to improve include absenteeism, depression symptoms and health-related quality of life (HRQOL). Hypothesis 2 is that the return on investment (ROI in the V-WHI at time T1 will be positive, exceeding 1). Analysis of ROI will be contingent upon confirmation of Hypothesis 1. ROI will be estimated based on the marginal group difference in productivity (presenteeism and absenteeism combined) relative to the marginal V-WHI program costs.
- K. Primary Outcome Variable(s): (Define the primary outcome variable(s) used to support the study objectives (e.g. if the objective is to show that treatment A is superior to treatment B in the treatment of subjects with essential hypertension, the primary outcome variable is blood pressure measurement.) The main variables for outcomes analysis quantify health-related decrements in work performance and productivity (presenteeism). In addition, we will assess work loss and work retention based on employment status and other work outcomes such as weekly hours. To help us interpret the scores, we have extensive comparative data from clinic and population-based samples for the Work Limitations Questionnaire (WLQ), the WLQ Time Loss Absence Module,(11;12) and other employment status items (e.g., job loss).

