  - 3.2. Explain the expected duration of subject participation including any follow-up. Each V-WHI subject requires 4 months of intervention. A booster session for V-WHI subjects will be provided at 8 months post-baseline. At the end of the first intervention period, which is month 4 to 5, all subjects will be invited to complete the first follow-up survey (T1). At month 9 (T2), all subjects will be invited to complete a final follow-up survey.
  - 3.3. Specify the projected date of completion of the proposed study. 11/30/2017

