**Power Analysis and Sample Size** 

In this study, we wish to power the study to obtain an effect size that represents a minimally clinically important difference on the health outcomes and an economically important difference related to work productivity impact (the primary endpoint). Currently, MCID is established for the PHQ-9(2) and the PCS and MCS for the VR-12.

For the PHQ-9, we anticipate that the average subject will have an average baseline score of 15 on a 0-27 scale. A clinically-meaningful reduction of 5 points, which is stated in the literature, would have 100% power to be detected. For PCS and MCS, a clinically-meaningful 5-point improvement would afford 99% power.

With regard to Hypothesis 2, corresponding to the study's power to detect an economically important difference, the primary criterion is whether an ROI greater than 1 can be obtained. This analysis is described in the following section.

For presenteeism, a reduction of 1.2% in productivity loss (or a relative improvement of 1.2%) would have comparable value to the maximum expected cost of treatment, meaning that the economic value of treatment would exceed the cost. A sample size of 100 treatment and 100 controls after subject dropout would achieve an 83% power for this outcome. To be sure of getting these numbers based on previous success rates, we will recruit 250 subjects prior to 50-50 randomization within full time and part time strata.

4.2. Define plans for data and statistical analysis, including key elements of the statistical plan, stopping rules and endpoints.

In this section, we describe the methods for testing hypothesis 1, several additional analyses including testing related to the secondary study outcomes and sensitivity testing related to both the primary and secondary study endpoints and statistical power calculations. Following this section, there is a description of the methods for testing hypothesis 2, which consists of the ROI analysis.

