### Aim1. Hypothesis 1.

The primary hypothesis of the study is that presenteeism, measured by the WLQ productivity loss score (PL), will be lower in the first (T1) follow-up for the V-WHI treatment compared with IC only. Productivity loss is computed using data

from the WLQ's four work limitation scales and then applying an empiricallybased algorithm to the scale scores. Details of the study on which the scoring methodology was based are included in Lerner et al, 2003.(12)

For hypothesis 1, the null hypothesis that the two groups are equal. The null hypothesis is tested by fitting the ANCOVA equation:

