### Aim 1. Secondary Analyses

In this section we discuss: 1) analysis of secondary outcomes, 2) analysis of T2 outcomes, and 3) sensitivity testing of outcomes (other than the primary outcome) These include: absenteeism (time missed and productivity loss – the ratio of time missed to time expected to work), combined productivity loss due to presenteeism and absenteeism, unemployment at follow-up, job turnover, individual WLQ scale scores, the PHQ-9 severity score, and the VR-12 PCS and MCS. These are considered secondary outcomes. The impact of the V-WHI on the secondary outcomes will be tested using ANCOVA models similar to those mentioned in the discussion of the study's Hypothesis 1 analysis.

Testing for T2 outcomes (instead of T1) will determine if the intervention effects observed at T1 are maintained. These analyses will use ANCOVA models similar to those described above and applied to all outcomes.

For the additional sensitivity analyses, the methods will be similar to those described for the hypothesis 1 study endpoint. In addition, we will conduct additional analyses to address some specific issues not addressed in relation to the primary study endpoint. For example, regarding productivity loss due to absences (time missed/time expected to work), previous studies suggest that the distribution of the data is heavily skewed to the right, i.e., more people are centered around average of 10% and a few people tend to have rather large values towards 100%. In regard to that, we will specify transformations of the absenteeism data to reduce the undue influence of long right tails. Another example pertains to self-report. Because key primary and secondary outcomes will be assessed from questionnaires, and the treatment cannot be effectively blinded, we will test for self-report bias. For this purpose, we can look at job loss during the post-baseline period. Job loss is a good candidate for this test because it is not an evaluative variable, but an event report. While job losses are expected to occur relatively infrequently in the study time period, we may have enough cases by final follow-up to conduct this analysis. The strong relationship between self-reported functioning, PHQ-9, and WLQ outcomes at T1 and loss of job at T2 should be equally strong in both the treatment and control groups. If treatment subjects who lose their jobs have lower WLQ and PHQ-9 scores at T1 then we would suspect that the reported scores at T1 are too low.

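### The job-loss check for self-report bias cannot tell a true V-WHI benefit from under-reporting: name the comparator and condition on both T1 scores

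*Combined protocol and SAP*

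**What the plan says.** Because key outcomes come from questionnaires and treatment cannot be blinded, Aim 1, Secondary Analyses (section W.4.2), proposes using job loss, an event rather than a self-rating, to look for self-report bias. It expects that the relationship between T1 scores and "loss of job at T2 should be equally strong in both the treatment and control groups". It then gives its only decision rule: "If treatment subjects who lose their jobs have lower WLQ and PHQ-9 scores at T1 then we would suspect that the reported scores" understate the true ones. The text does not say lower than whom, and gives no model or threshold. It adds that "we may have enough cases by final follow-up to conduct this analysis".

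Elsewhere the plan predicts the same pattern as a treatment effect. Under Aim 1, Hypothesis 1, the WLQ productivity loss score (PL) "will be lower in the first (T1) follow-up for the V-WHI treatment compared with IC only". Section J expects depression symptoms to get better at T1 as well.

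**The concern.** Lower PL and PHQ-9 scores are better scores. If V-WHI works, the treated T1 distribution moves down, and treated subjects who later lose their jobs move down with it. If V-WHI does nothing but treated subjects report too favourably, treated job-losers also score lower. The rule attaches one of these two explanations to a pattern that both produce.

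This is the only check the plan describes for self-report bias in an unblinded, self-reported primary outcome. Followed as written, it would cast suspicion on the benefit the trial is designed to find.

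**Working it through.** **Inputs from the plan.** The shift is 1.2 PL points (Power Analysis and Sample Size). The same section states: "A sample size of 100 treatment and 100 controls after subject dropout would achieve an 83% power for this outcome". No SD is given. Power = Φ(1.2/(SD·√(2/100)) − 1.96) reaches 83% at SD 2.91; SD 3.5 gives 68% and SD 4 gives 56%. The 83% can therefore be back-solved but not reproduced. The only job-loss rate is from an earlier study (Background): "within six months after enrolling in the study, 15% of the depression group became unemployed".

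**Assumptions.** SD 2.9 to 6; control job-loss risk 12% (range 10 to 20%); gradient g = log odds ratio of job loss per SD of true PL, 0.3 to 4.

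**Step 1: the plan's rule.** True PL = SD·z − e·arm. Reported PL = true − u·arm. Logit P(job loss) = a + g·true/SD. A real benefit is e = 1.2, u = 0; pure under-reporting is e = 0, u = 1.2. Mean reported PL among job-losers, treated minus control, by numerical integration:

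| g | real benefit | under-reporting |
|---|---|---|
| 0.3 | −1.19 | −1.20 |
| 0.6 | −1.15 | −1.20 |
| 1 | −1.06 | −1.20 |
| 2 | −0.74 | −1.20 |
| 4 | −0.39 | −1.20 |

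The last column is exact: true scores do not differ by arm, and every treated report is 1.2 lower. Over the SD and risk ranges the entries move by at most 0.04. The sizes separate only for steep gradients; the sign never does.

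**Step 2: equal slopes.** Under under-reporting, substitute true = reported + u·arm: logit = a + g·reported/SD + (g·u/SD)·arm. The slope is the same in both arms and only the intercept moves, by g × 1.2/SD. For g = 1 that is 1.2/2.9 = 0.41, 1.2/4 = 0.30 or 1.2/6 = 0.20. Under a real benefit acting only through PL, the arm term is 0. In simulations at 100 or 140 per arm, an arm-by-score interaction test rejected in about 4 to 5% of trials whether there was a benefit, a bias or neither. The information lies in job-loss risk at equal reported score.

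**Step 3: why both scores in one model.** The plan expects PL and PHQ-9 both to improve. Take its 1.2 and 5 points, with assumed SDs 4 and 5 (shifts 0.30 and 1.00 SD), correlation 0.5, honest reporting, and job loss depending on each score with gradient g. To first order the arm coefficient is:
- PHQ-9 only: g(0.5 × 1.00 − 0.30) = 0.20g, so +0.10 at g = 0.5 and +0.20 at g = 1 (simulated +0.10 and +0.18).
- PL only: g(0.5 × 0.30 − 1.00) = −0.85g, so −0.43 and −0.85 (simulated −0.42 and −0.77).
- Both scores: about 0.

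A PHQ-9-only model can thus show excess treated job loss with no misreporting. A PL-only model can hide misreporting: with PL under-reported by 1.2 and a real 2.5-point PHQ-9 gain, it gives −0.02 and −0.04. The two-score model gave +0.14 to +1.27 in the under-reporting scenarios simulated.

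**Step 4: how many events.** T1 is at month 4 to 5 and T2 at month 9. Applying the earlier study's rate to 200 subjects:
- T1 at month 4: 200 × 0.85^(4/6) = 179 employed; × (1 − 0.85^(5/6)) = 12.7%, about 23 later losses.
- T1 at month 5: 200 × 0.85^(5/6) = 175 employed; × 10.3%, about 18 losses.
- Both sites pooled (350 × 0.8 = 280, same attrition assumed): 25 to 32 losses.

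At 175 to 179 subjects (SD 4, g = 0.6 to 2), treated job-losers scored lower in 68 to 75% of simulated trials with a real benefit, 73 to 82% with under-reporting and 48 to 50% with neither. Conditioning on reported PL and baseline PL, the arm coefficient was positive in 48 to 51% (real) against 63 to 85% (under-reporting). Its power was 5 to 17% for a 1.2-point bias and 16 to 87% for 4 points. The two-score model was not simulated at this size. It has five coefficients besides the intercept, so about 18/5 = 3.6 to 23/5 = 4.6 events for each.

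**The case against.** *The preceding sentence may already intend the right comparison.* If equally strong means the same risk at the same score, level included, the closing rule could be read as treated job-losers scoring lower than that common relation implies. That would be the right comparison. But the text does not say so, and the rule looks only at job-losers' scores.

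*Another comparator may be meant.* Against treated subjects who kept their jobs, a uniform benefit would not trigger the rule. Nor would uniform under-reporting, since both groups shift together. The sentence needs a comparator on any reading.

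*Other evidence is planned.* Unemployment and job turnover are compared by arm as secondary outcomes. A benefit acting on retention could show there; pure under-reporting would not. This stands, and the comparison belongs beside the check. With so few events it will be imprecise.

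*The replacement is weak and not clean.* This also stands. V-WHI works on work methods and conditions, so a direct effect on retention is plausible. In the PL-only model at SD 4, a direct odds ratio of exp(−g × 1.2/4) = 0.84, 0.74 or 0.55 (g = 0.6, 1, 2) would cancel a 1.2-point bias exactly. The 15% rate may also be optimistic, since the plan itself expects few job losses.

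*The check is tentative and exploratory.* True, and this sets the priority.

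**Conclusion.** The rule as written is wrong in a limited way: the signal is non-specific as to cause. On the treated-versus-control reading, a true benefit gives the same sign as under-reporting and, for g up to about 1, nearly the same size (−1.06 to −1.19 against −1.20). The sign result follows from the plan's own hypotheses; the sizes rest on assumed gradients and job-loss rates.

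A reader might infer more than the documents support:
- That the primary result is at risk. It is not: no decision follows from the check, and neither the Hypothesis 1 test nor the condition for running Hypothesis 2 uses it.
- That the sizes always coincide. They diverge for steep gradients (−0.39 against −1.20 at g = 4).
- That excess treated job loss at equal scores would prove under-reporting. It would only be compatible with it, given the assumption that V-WHI affects job loss through the two measured scores alone.

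Low priority, but worth correcting before outcome data are seen, so that the interpretation is not chosen afterwards.

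**What to change.** Replace the closing sentence of the self-report paragraph with:

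> Lower T1 scores among treated than control job-losers are also expected if V-WHI works, so they will not by themselves be read as bias. Among subjects employed at T1, we will fit one logistic regression of job loss after T1 on arm, reported T1 PL and T1 PHQ-9 together, and their baseline values. More job loss in V-WHI than the reported scores jointly predict (a positive arm coefficient) would be compatible with under-reporting. The estimate and 95% CI will be reported as exploratory, beside the by-arm comparison of unemployment. This reading assumes that V-WHI affects job loss only through these scores; a direct effect on job retention, another mediator or measurement error can mask or mimic bias. A null result does not exclude bias, because few job losses are expected.

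Do not fit PL and PHQ-9 in separate models, for the reason in Step 3.

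The cost is a short rewrite and one extra regression on data already scheduled: Table 1 has WLQ, PHQ-9 and employment items at baseline, T1 and T2. The downside is low power and few events per coefficient, so the analysis can reveal only gross bias.

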### The Cognitive-Behavioral Therapy (CBT) Component of V-WHI

Depression frequently involves maladaptive cognitions and behaviors that may interfere with working and contribute to depressive symptoms. Veterans, therefore, may benefit from developing a new repertoire of more positive, adaptive coping strategies. In this V-WHI component, counselors provide psychoeducation to veterans about CBT concepts such as the positive impact of being active and socially connected and ways in which negative self-talk can make depression worse and impair functioning. After discussing the CBT concepts and how they apply to the veteran, he or she will engage in exercises to practice more positive, adaptive behavioral and cognitive strategies in everyday life. Veterans then discuss the effectiveness and impact of these new strategies with their counselors. The veteran and counselor will engage in an ongoing, collaborative process of identifying maladaptive coping strategies, practicing new ones and monitoring progress. The V-WHI uses an adapted work-focused version of the manual, Creating a Balance(69).

To obtain the V-WHI, each veteran will be assigned to a study counselor who will provide the experimental treatment by telephone for 4 months. The V-WHI study counselors will not be involved in other aspects of the veteran's care. The initial 4-month period is designed to coincide with the acute phase of depression treatment. In order to support the gains made in V-WHI treatment, a booster session will be provided at 8 months post-baseline. During the initial intervention period, the veteran will have a 50-minute phone session with his or her assigned counselor every 2 weeks (for an 8-visit total). Between visits, the veteran will be asked to perform specific activities in support of treatment goals (i.e., homework). Because both V-WHI treatment components require the veteran to do homework and depression can undermine motivation, specific techniques are used to promote adherence to the care. In the V-WHI model, the counselors use Motivational Interviewing techniques to facilitate cognitive and/or behavioral change.(70) At the end of the initial intervention period, the counselor and veteran will co-write a customized self-care plan designed to maintain and extend progress. At month 8, the counselor and veteran will meet by phone to review progress (including administering the PHQ-9 and WLQ) and make any necessary adjustments in the self-care plan.

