A third sensitivity issue is related to the relationship of T1 and T2 outcomes and ways they might be characterized. For these purposes, we would analyze T2-T1 outcomes to state how well the results were maintained, or analyze all measurements jointly using mixed models where there are random effects due to subject, e.g.,

PLit= g\*X + g1\*X\*T1 + g2\*X\*T2 + a1\*T1 + a2\*T2 + c1\*T1\* I(V-WHI) + c2\*T2\* I(V-WHI) + ei + eit

where the subscript t refers to the time, 0, 1 or 2, and T1 and T2 are indicator variables corresponding to T1 and T2.

Hypothesis 2. Cost Benefit Analysis/ROI Determination.

We will analyze the ROI of the experimental program if Hypothesis 1 is confirmed and test whether, consistent with Hypothesis 2, the ROI to achieve productivity gain is greater than 1. The general approach will be to compute the cost and benefit components of the ROI. The ROI is computed as the incremental cost minus the incremental monetized benefit divided by incremental cost (amount invested in the new program). A ratio exceeding one indicates a favorable ROI. Our Hypothesis 2 analysis will consider only that portion of the intervention's incremental cost related to the V-WHI and will quantify incremental benefit as the monetized value of productivity improvements. We will not consider consumption of resources not directly related to depression because of the complexity and scope of that type of analysis in this population. Nor will we include subject costs and benefits. Subjects presumably engage in the intervention because the resulting additional functional effectiveness and well-being outweigh their incurred costs (e.g., the time consumed). While we could measure the costs incurred by veterans in the program, we cannot measure the corresponding functional benefits in their personal lives.

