Benefits: We will compute benefits by quantifying and monetizing two components of productivity loss: presenteeism and absenteeism. For each component, we will compare the average change in the usual care and V-WHI care groups. We estimate productivity losses due to presenteeism using a validated WLQ Productivity Loss algorithm. Absenteeism is computed as hours of missed work during the time period divided by hours usually worked during that time period. Each productivity loss component will be monetized by multiplying it by the sample's median (fully loaded) wage. We use the median wage because we expect the wage distribution to be right skewed, making the mean less representative of the typical worker.

The benefit (i.e., reduced productivity loss) for the V-WHI intervention can be computed as follows. Let  $\triangle AP$  be the reduction in the proportion of time absent for V-WHI compared to usual care, while  $\triangle PP$  is the corresponding reduction in productivity loss due to presenteeism (i.e., the reduction in the proportion of output lost to presenteeism while working). Let H be the number of work hours during the period, while W is the median fully loaded wage rate. Then saved hours of productive output for V-WHI is H x ( $\triangle AP+\Delta PP$ ). Multiplying this result by W yields the monetized value of the reduced productivity loss.

Costs: The intervention's incremental cost has three components: 1) The value of time counselors spend in training is the product of their (fully loaded) wage rate and the number of hours needed to complete training; 2) The incremental value of time counselors spend counseling is the product of their fully loaded wage rate and the additional hours they spend counseling (compared to usual care); 3) The incremental value of time patients spend being counseled is the product of their fully loaded wage rate (the median veteran wage) and the additional hours they spend in counseling (compared to usual care).

The most straightforward cost and benefit analysis would compare the value of the benefit (i.e., the value of the reduced productivity loss) to the incremental cost of counseling. Because of the project's scale, changes in benefits will then be compared with changes in incremental costs.

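### The ROI formula for Hypothesis 2 runs opposite to its exceeding-one rule, and the plan both excludes and includes patient time as a cost

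*Combined protocol and SAP*

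**What the plan says.** All places are in the Combined protocol and SAP.

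- **Formula and rule** (W.4.2, Hypothesis 2. Cost Benefit Analysis/ROI Determination): "The ROI is computed as the incremental cost minus the incremental monetized benefit divided by incremental cost", followed by "A ratio exceeding one indicates a favorable ROI".
- **Gate** (same section): "We will analyze the ROI of the experimental program if Hypothesis 1 is confirmed".
- **Benefit** (W.4.2, Benefits): the reductions in absence and in presenteeism loss, V-WHI against usual care, are added and multiplied by work hours and wage. "Let H be the number of work hours during the period, while W is the median fully loaded wage rate". The length of the period is not given.
- **Cost** (W.4.2): the Hypothesis 2 paragraph says "Nor will we include subject costs and benefits", with time consumed as its example of a cost that veterans incur. The Costs paragraph then lists a third component: "The incremental value of time patients spend being counseled is the product of their fully loaded wage rate".
- **Section J**: ROI at T1 is the group difference in productivity "relative to the marginal V-WHI program costs", expected to be positive and above 1.
- **Power section (W.4.1)**: a 1.2% reduction in presenteeism loss is said to be worth about the maximum expected treatment cost.
- **Section O, Data Collection**: delivery cost rests mainly on counselor and clinical supervision hours. Supervision is not among the three components in the Costs paragraph.

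**The concern.** A return measure should rise with benefit. This one falls, yet a high value is called favorable. Followed literally, a program that pays for itself fails Hypothesis 2, which is the whole of Aim 2. An analyst who sees the slip has to choose a replacement, and the obvious ones give different verdicts. The same holds for patient time, which is excluded in one paragraph and counted in another. If either choice is made once the data are visible, the Aim 2 conclusion no longer follows from a prespecified rule.

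**Working it through.** **Plan's own figures.** The plan gives no numerical ROI. Its nearest figure is 83% power for the 1.2% presenteeism reduction with 100 per group. No SD is stated, so this can only be solved backwards: 1.2 × √50 / (1.960 + 0.954) = 2.91 points. Nothing below depends on it.

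**Step 1: the rule as written.** Let C > 0 be incremental cost and B = H × W × (ΔAP + ΔPP) the benefit, positive when V-WHI reduces loss. Then (C − B)/C = 1 − B/C, and 1 − B/C > 1 if and only if B < 0.

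| True B/C | As written, (C − B)/C | Sign reversed, (B − C)/C | Ratio, B/C |
|---|---|---|---|
| 0 | 1 | −1 | 0 |
| 0.5 | 0.5 | −0.5 | 0.5 |
| 1 | 0 | 0 | 1 |
| 1.5 | −0.5 | 0.5 | 1.5 |
| 2 | −1 | 1 | 2 |
| 3 | −2 | 2 | 3 |

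The written form never exceeds 1 in this table. The sign-reversed form exceeds 1 only if B > 2C. The plain ratio exceeds 1 when B > C, which is the only version that fits section J and the power section. For a true B/C between 1 and 2, the choice of repair decides Hypothesis 2.

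Reading the sentence without brackets, as C − (B/C), does not help. A money amount minus a pure number has no consistent unit. With C = 1,000 (assumed), B/C = 0.5 gives 999.5 and B/C = 5 gives 995, so the value still falls with benefit and passes the threshold whatever the benefit is.

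**Step 2: effect of the gate.** Once Hypothesis 1 is confirmed, ΔPP > 0. B < 0 then requires ΔAP < −ΔPP, so absenteeism must worsen by more than presenteeism improves. With ΔPP = 1.2 points and 40 h/week (assumed) over 4 months (17.33 weeks), H = 40 × 17.33 = 693 h. V-WHI veterans would have to miss more than 0.012 × 693 = 8.3 extra hours for the written rule to be met.

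**Step 3: size of the patient-time item.** The CBT component section sets eight 50-minute sessions: 8 × 50/60 = 6.67 h. Benefit and patient time are both valued at the median veteran wage, so the wage cancels. The gain needed to offset this item alone is 6.67/H.

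| Hours per week | Source | H, 4 months | Points needed | H, 5 months (21.67 weeks) | Points needed |
|---|---|---|---|---|---|
| 15 | eligibility minimum (R.2.1.1) | 260 | 2.56 | 325 | 2.05 |
| 30 | full-time cut-off (M.2.2) | 520 | 1.28 | 650 | 1.03 |
| 40 | assumed | 693 | 0.96 | 867 | 0.77 |

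A 1.2-point gain over 4 months is worth 3.12, 6.24 and 8.32 hours in the three rows. Patient time is therefore 214%, 107% and 80% of it. Over 9 months with the booster session added (9 × 50/60 = 7.5 h), the shares are 107%, 53% and 40%.

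**The case against.** The strongest reply is that the formula is a visible drafting slip. Section J, the power section and the end of the Costs paragraph, which sets the value of the benefit against counseling cost, all show the intended direction, so no sensible analyst would apply the sentence literally. That is probably right about intent. It does not settle the rule, because nothing corrects the sentence, section J's pairing of positive with exceeding 1 mixes two conventions, and the natural sign repair doubles the hurdle.

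The patient-time figures can also be challenged. The 1.2% is tied to the maximum expected cost, concerns presenteeism only, and has no stated period, while B also counts absenteeism. The plan also words it as a relative improvement, so reading it as 1.2 percentage points is an assumption. A longer benefit period shrinks the item: over 9 months at 40 h/week it needs 7.5/1,560 = 0.48 points. The 15 h/week row is the eligibility floor, not a likely average. These cautions stand, and the figures are illustrative. The 4 to 5 month horizon is still the better reading, since section J places the ROI at T1. The contradiction about patient time does not depend on any of them.

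**Conclusion.** The concern holds. As written, the Hypothesis 2 rule is met only if V-WHI increases combined productivity loss. After a confirmed Hypothesis 1, that needs an absenteeism increase larger than the presenteeism gain. This conclusion is algebra and assumes only C > 0 and the plan's own definition of benefit.

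The cost term is also contradictory. Over 4 to 5 months, counting patient time requires 0.77 to 2.56 points of productivity, depending on weekly hours, so including or leaving it out could decide the result. That range assumes all eight sessions are attended, BHL counseling time is equal in both groups, benefit runs from baseline to T1, and the booster is left out.

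The damage is confined to the contingent Aim 2 conclusion. The Hypothesis 1 test is untouched. This should be fixed.

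**What to change.** 1. In W.4.2 replace the formula with: ROI = incremental monetized benefit / incremental cost, favorable if above 1. The equivalent is (benefit − cost)/cost, favorable if above 0. Change formula and threshold together, and use the same definition in section J.
2. Agree one cost list before outcomes are compared by group. Either drop patient time from the Costs paragraph, or lift the exclusion of subject costs for that item. State whether clinical supervision hours count, so that section O and W.4.2 agree.
3. State the length of the period that defines H.
4. In W.4.1 say which cost components the 1.2% figure covers.

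The cost is a few sentences and one decision on patient time, plus the supervision item. It needs no new data and no change to the Hypothesis 1 analysis.
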